### **5.4 Sample size justification for secondary distribution cohorts (quantitative data collection)**

The primary aim of secondary distribution is to increase uptake of HIV testing services among the intended users. Through the secondary distribution cohorts, we will investigate factors associated with use of an HIVST as reported by the index individual. To meet this aim, our sample size is based on two key factors considered *a priori* to influence reported use of the HIVST: knowledge of partners HIV status in the ANC cohort and HIV status disclosure in the cohort of individuals who know their HIV-positive status. There limited evidence of factors associated with use of a secondary distribution HIVST. However, in both groups, we anticipate that reported use of the HIVST will be approximately two-times higher among pregnant

women who state they know their partners HIV status and among HIV-positive individuals who have disclosed their HIV status to their partner.

In a cohort study among women attending ANC in Kenya, ~87% reported distributing the HIVST to their primary partner and that the partner used the HIVST [14]. This was in a clinical trial scenario and so using this figure and extrapolating to a more real life scenario, we hypothesise that in this study among individuals who accept an HIVST, ~60% of women in ANC who report knowing their partners HIV status and ~60% of individuals who report having disclosed their HIV-positive status to their partner will report that their partner used the HIVST at 1-month follow-up. To be conservative in our estimates, we have assumed that 40% of those not reporting these factors will report that their partner used the HIVST. Based on these estimates we require a sample size of approximately 300 per cohort (~600 total) to have at least 80% power to detect this association at the p=0.05-level.

We anticipate that up to 30% of individuals who accept the offer may be lost to follow-up. To account for this potential loss to follow-up, we will therefore recruit approximately 450 individuals per cohort (approximately 900 individuals total) to maintain at least 80% power to detect this association at the p=0.05-level.

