### Appendix 3: Quantitative data collection tools

Appendix three includes the questions that will be asked to the participants who will be recruited in the quantitative cohort.

***Please note: these questionnaires are presented to inform readers of the wording of the questions. The response options, order and skip patterns are subject to change once programmed on electronic data capture devices.***

**“Exit” Interview Quantitative Cohort Questionnaire (Questions to be asked at the time of distribution – whether at ANC or ART)**

Section 0: Preparing for the survey			
Variable Name	Question	Options	Option Codes
PS 1	What is the date today?	[time stamp]	
PS 1a	CLINIC NAME	[EDC CODE]	
PS 2	Scan participant barcode		
PS 3	Which community are you in?	Community 1	1
		Community 2	2
		Community 3	3
		Community 4	4
		Community 5	5
		Other	Specify
PS 4	What models of HIV self-testing distribution are in this community? [tick all that applies]	VMMC	1
		Community- or facility led	2
		Secondary distribution through ANC	3
		Secondary distribution HIV testing and treatment services	4
		Workplace	5

		Other (Specify)	6
PS 5	Through which distribution model was the client offered an HIV self-testing kit?	Secondary distribution through ANC	3
		Secondary distribution through HIV testing and treatment services (ART and VCT)	4
Section 1: Consenting Process			
Consent 1	I would like to take some time to explain the research that we are carrying out in this study about HIV self-testing.  At the end of my explanation, you can decide whether you would like to participate and continue with answering specific questions for the study. Before we begin, do you have any questions?		
Consent 2	Obtain consent using the consent form written in the language that the participant understands		
Consent 3	DID THE INDIVIDUAL GIVE CONSENT TO PARTICIPATE IN THE STUDY?	No	0
		Yes	1
Section 2: Demographics			
	Today's date	Auto complete by EDC	
Demo 1	Sex	Male; Female	1;2
Demo 2	What is your date of birth?	DDMMYYYY	01011900 if unknown
Demo 4	How long have you been living in [NAME OF CURRENT PLACE OF RESIDENCE]?	Years: months	

Demo 5	How many minutes did it take you to come to the health facility?	TIME (minutes)	
Demo 6	What form of transport did you use?	Came on foot	
		Taxi	
		Private car	
		Bus	
		Bicycle	
		Other	

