H_HIVCT 16	How can you best describe your partner's main income generating activity or work status?	Farmer (own land); Farm work on employer's land; Domestic; Work in bar, hotel, guest house; Fishing; Mining; Working in shop; Informal Selling; Transport (trucker, taxi driver); Factory; Guard (security company); Police/soldier; Clerical and office work; Government; Teacher; health care; Other Professional; Other (Specify)	
H_HIVCT 17	How do you rate your partner's general health?	Very good; good; fair; poor; very poor	1;2;3;4;5
H_HIVCT 18	On average how many nights a week does your partner spend away from home for work, if at all?	0 (no nights away from home), 1, 2, 3, 4, 5, 6, 7	
H_HIVCT 19	Have you ever discussed HIV testing with your partner?	No; Yes	0; 1
H_HIVCT 20	Has your partner ever had an HIV test?	No; Yes; Don't know	0; 1; 2
H_HIVCT 21	When was the last time that your partner tested for HIV?	Year; month	

H_HIVCT 22	Do you know the result of your current partner's most recent HIV test?	No; Yes	0; 1
H_HIVCT 23	What is the HIV status of your partner?  INTERVIEWER: REMIND PARTICIPANT THAT THEY DO NOT HAVE TO ANSWER THIS QUESTION IF UNCOMFORTABLE. IF SHE SAYS THAT SHE KNOWS BUT DOESN'T WANT TO SHARE – THIS IS CODE 3. IF THE PERSON TESTED BUT DID NOT SHARE THE RESULT WITH THEM SO THEY DON'T KNOW, THIS IS CODE -1	Positive; Negative; partner has not tested (unknown); Partner tested – I know the result but I don't wish to share Don't know; Partner tested – but I don't know the result	1; 2; 3; 4; -1
H_HIVCT 24	Were you offered an HIVST to give to your partner?	No; Yes	0; 1
H_HIVCT 25	Did you accept the offer of an HIVST for use by your partner?	No; Yes	0; 1
H_HIVCT 26	If no, why did you not accept the offer of an HIVST for your partner?	Need partner's permission to take HIVST; Partner recently HIV tested; Partner not interested in HIV testing	
H_HIVCT 27	Before the offer of an HIVST for your partner, had you ever heard of HIVST?		
H_HIVCT 28	Do you think your partner will be comfortable receiving the HIV self-test kit from you?	No; Yes; Don't know	0;1; -1
H_HIVCT 29	If No, why would your partner be un-comfortable to receive the test kit from you?		
Section 5: Question on Intimate Partner Violence			
QIPV 1	If you told your partner that you are visiting the health facility today. And one of the services you	No; Yes; Don't know	0;1; -1

	will receive will include HIV testing, would he react angrily or negatively?		

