Use_HIVST 3	Did you give your partner an HIV self-test kit that you collected on his behalf?	No; Yes	0; 1
Use_HIVST 3a	If no, why did you not give the HIVST to your partner?	I lost the kit; my partner already knows his/her HIV positive status; I feared my partner would get angry; my partner has been away from the time I collected the test kit; my partner and I are no longer in partnership; other (Specify); refuse to respond	1; 2; 3; 4; 5; 6; 7
Use_HIVST 4	Did your partner use the HIV self-test that you gave him?	Yes – I was present when he used the self-test; Yes – I was told that the self-test kit was used; No- he did not use the self-test kit; I Don't know	1; 2; 3; 4
Use_HIVST 5	What was the date that your partner used	Year; month; day	

	the HIV self-test kit?		
Use_HIVST 6	When your partner used the self-test, did you also use a self-test at the same time?	Yes (Couple testing); No; Don't know	1; 2; 3
Use_HIVST 7	What were the results of your self-test?	HIV-positive; HIV-negative; Indeterminate; Don't know; Refused to answer	1; 2; 3; 4; 5; 6
Use_HIVST 8	Do you know the results of your partner's HIV test?	No; Yes; Don't know; Refused to answer	1; 2; 3; 5
Use_HIVST 9	What was your partner's test result?  Interviewer: Remind participant that they do not have to answer this question if uncomfortable. If she says that she knows but doesn't want to share – this is code 99. If the person tested but did not share the result with them so they don't know, this is code 98	HIV-positive; HIV-negative; Indeterminate; Don't know; Refused to answer	1; 2; 3; 4; 5
Use_HIVST 10	Did your partner go to a clinic or health facility in order to confirm the result that was obtained from the self-test (confirmatory testing)?	No; Yes; Don't know	0; 1; 2
Use_HIVST 11	Did your partner go to a clinic or health facility for HIV care?	No; Yes; Don't know	0; 1; 2
Use_HIVST 122	Is your partner currently in ART care?	No; Yes; Don't know	0; 1; 2
Use_HIVST 13	Did your partner go to the clinic or health facility for HIV prevention services?	No; Yes; Don't know	0; 1; 2
Use_HIVST 14	What HIV prevention services did they go for?	VMMC; to collect condoms; other (specify)	0; 1; 2

Social Harms/benefits Screening at follow-up visit			
Variable Name	Question	Options	Option Codes

SHS_Fu_1	When you gave your partner the HIV test kits, did you explain that it is for HIV testing?	Yes; No; Don't know	1; 2; 3

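### In exit-interview item H_HIVCT 23 the interviewer note and the code list disagree: the note sends a woman who knows her partner's HIV status but will not share it to code 3, which the list reserves for an untested partner

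*Protocol*

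**What the plan says.** All of this is in the Protocol; the first four places are in Appendix 3.

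- **H_HIVCT 23, interviewer note:** "IF SHE SAYS THAT SHE KNOWS BUT DOESN'T WANT TO SHARE – THIS IS CODE 3". The note's other half sends a woman whose partner tested but did not tell her the result to code -1.
- **H_HIVCT 23, options:** the list opens "Positive; Negative; partner has not tested (unknown" and goes on to "Partner tested – I know the result but I don't wish to share", then the categories for not knowing. The printed codes are 1; 2; 3; 4; -1.
- **H_HIVCT 22, the item just before:** "Do you know the result of your current partner's most recent HIV test", answered No (0) or Yes (1). H_HIVCT 20 asks whether the partner has ever had an HIV test.
- **Opening note of the appendix:** "The response options, order and skip patterns are subject to change once programmed on electronic data capture devices".
- **Section 5.4:** the ANC cohort is sized on "women in ANC who report knowing their partners HIV status". About 60% of them are expected to report that the partner used the kit, against 40% of the others. About 300 followed per cohort are to give at least 80% power at p=0.05, and about 450 are recruited to allow for up to 30% loss.
- **Use_HIVST 9, follow-up form (Appendix 3):** for a woman who knows the result but will not share it the note says "this is code 99", and it uses 98 where the result was not shared with her. The printed codes for that item run from 1 to 5.

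**The concern.** The note and the list give two different codes for the same answer. A research assistant who follows the note stores a woman who knows her partner's status under the code for a partner who has never been tested. After that, code 3 cannot be interpreted from H_HIVCT 23 alone.

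The item is close to the main ANC exposure. An analyst who built knowledge of partner status from H_HIVCT 23, counting codes 1, 2 and 4 as known and 3 and -1 as not known, would move some women who know into the comparison group. Their higher expected rate of reported use would pull that group upward and narrow the difference the cohort is meant to detect. The error is made at data entry, so an analysis plan can repair it afterwards only by using other items.

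**Working it through.** **1. Matching codes to options, in printed order**

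| Code | Option in the list | What the note says |
|---|---|---|
| 1 | Positive | – |
| 2 | Negative | – |
| 3 | Partner not tested | Knows, will not share |
| 4 | Knows, does not wish to share | – |
| -1 | Does not know / tested, result not known to her | Tested, result not shared with her |

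The text after the fourth option runs together in the extracted table, so the match is by position. However that text is split, the third option remains the untested partner. The note's second half agrees with the list, so the discrepancy is a single digit.

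**2. The plan's own sample size**

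Inputs from section 5.4: p1 = 0.60, p2 = 0.40, alpha 0.05 (two-sided assumed, since sidedness is not stated), power 0.80. The pooled two-proportion formula for equal groups gives

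n per group = [1.96·√(2·0.5·0.5) + 0.842·√(0.6·0.4 + 0.4·0.6)]² / 0.20² ≈ 97, or 194 in total.

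A 1:4 split needs 60 + 240 = 300, which is the stated figure. So 300 gives at least 80% power whenever the share who know lies between 20% and 80%. For loss, 300/0.70 = 429, rounded up in the plan to about 450; 450 × 0.70 = 315. The coding discrepancy does not change any of these figures.

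**3. Effect if the factor came from H_HIVCT 23**

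Let s be the share who truly know and m the share of those who withhold and are entered as code 3. The documents give neither, so both are assumptions. I also assume that women who withhold have the same 60% use rate as others who know. With N = 300:

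- recorded as knowing: k = 300·s·(1−m), use rate 60%
- recorded as not knowing: u = 300 − k, use rate [300·s·m·0.60 + 300·(1−s)·0.40] / u

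For s = 50%:

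- m = 10%: k = 135, u = 165, rate (9 + 60)/165... that is (15·0.6 + 150·0.4)/165 = 41.8%, difference 18.2 points, power 88%
- m = 20%: k = 120, u = 180, rate (30·0.6 + 150·0.4)/180 = 43.3%, difference 16.7 points, power 81%
- m = 30%: k = 105, u = 195, rate (45·0.6 + 150·0.4)/195 = 44.6%, difference 15.4 points, power 72%

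Power for other shares, each beside its own baseline:

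| Share who know | m = 0 | m = 10% | m = 20% | m = 30% |
|---|---|---|---|---|
| 20% | 80.0% | 74.7% | 68.5% | 61.6% |
| 50% | 93.8% | 88.4% | 81.1% | 72.3% |
| 70% | 89.4% | 77.9% | 65.4% | 53.4% |

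**4. Effect if the factor came from H_HIVCT 22**

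A woman who knows the result but will not disclose it answers Yes on H_HIVCT 22, whatever is entered on H_HIVCT 23. Nobody is moved, and the m = 0 column applies.

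**The case against.** A reader might infer that the note necessarily puts women who know into the not-known group for the sizing factor, and that the ANC cohort is therefore underpowered. The documents do not support that. Section 5.4 describes the factor as reported knowledge, which is close to what H_HIVCT 22 asks, and nothing in the protocol derives it from H_HIVCT 23. The two items are not identical, since 22 refers to the most recent test and 23 to status, so use of 23 is conceivable, but it is not stated. Which item defines the exposure may properly be settled in an analysis plan that is not shown, so its absence here is not a fault.

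Nor does it follow that the count of untested partners is spoiled beyond repair. H_HIVCT 20 records testing directly, and a miscoded woman would have Yes on 22 with code 3 on 23, a combination that can be found. Section 6.3 provides for daily error checks.

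The appendix also says that the form is provisional. That helps less: the caveat names response options, order and skip patterns, not interviewer instructions, and a wrong instruction may be carried over unnoticed.

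The 98 and 99 codes in Use_HIVST 9 lie outside that item's list and cannot be mistaken for a valid answer. They are untidy and misclassify nobody.

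**Conclusion.** The contradiction within H_HIVCT 23 stands: by the printed list the code should be 4, and the note says 3. Followed as written, code 3 mixes two opposite kinds of answer. The consequence for the ANC comparison is conditional. It is zero if knowledge of partner status is taken from H_HIVCT 22. If H_HIVCT 23 were used instead, power at 300 followed would fall from about 94% to between 88% and 72%, assuming that half the women know, that 10% to 30% of them withhold, that those who withhold have the same 60% use rate, and that the test is two-sided. The stated sample size is unaffected. This is a minor correction to make before the form is programmed.

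**What to change.** - In the H_HIVCT 23 note, change code 3 to code 4 so that it matches the list.
- Take knowledge of partner status from H_HIVCT 22 (Yes = known), and say so wherever the exposure is defined.
- Add an electronic check that flags H_HIVCT 22 = Yes together with H_HIVCT 23 = 3. By the printed list the two answers cannot both be true.
- As a tidy-up, align the 98 and 99 codes in the Use_HIVST 9 note with its printed list.

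The cost is one digit, one sentence, one check and a small edit to the follow-up form. If interviews have already been done under the printed note, the same combination of answers identifies the records to review.

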**Figure 2: Schematic of the quantitative and qualitative cohort in ANC and ART models**

For the secondary distribution cohorts, we will measure individual- and couple-level factors associated with acceptability to the index patient and intended user including: sex, age, previous HIV testing history, newly diagnosed or previously undisclosed HIV, relationship of the distributor and intended user (including type of relationship, age differential, measures of equality and empowerment), history of gender based violence and clinic from which the Index was recruited (ANC or HIV testing and treatment services).

The primary outcome of the secondary distribution cohorts is the:

- 1) Proportion of index patients who accepted an offer of secondary distribution HIVST kit(s) who report that their sexual partner(s) used the HIVST kit,

Secondary outcomes are the:

- 1) Proportion of index patients accepting an offer of HIVST kit(s) for secondary distribution,
- 2) Proportion of index patients who accepted an offer of a secondary distribution HIVST kit(s) who report that their partner used the HIVST kit(s) and linked to prevention or care services within 1-month of distribution

- 3) Proportion of intended recipients who self-report a) having used an HIVST kit and b) having attended confirmatory HIV testing, or HIV prevention or HIV care services within 3-months of distribution.

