## **5.2 Recruitment of secondary distribution cohorts**

For the secondary distribution cohorts, consecutive study participants will be recruited as they exit their clinical consultation at ANC or HIV testing and treatment services. The staff in charge of HIVST distribution will refer all individual who are offered an HIVST for secondary

distribution. Willing potential study participants will then be referred to Zambart Research Assistants (RAs). To facilitate good rapport between research staff and clinic attendees, the staff in charge of HIVST distribution will introduce the individuals to the study RA.

After introductions, the study RAs will provide detailed information about the study and request written informed consent. They will then administer an “exit” interview. The exit interview will include socio demographic factors, history of HIV testing, and their partners’ history of HIV testing, details about their relationship with their partner including questions about gender based violence and whether they were offered a secondary distribution HIVST. If they were offered secondary distribution HIVST they will be asked whether they accepted or declined the offer of a secondary distribution HIVST and the reasons influencing their decision.

After completion of the exit interview, individuals reporting that they accepted the HIVST for secondary distribution will be asked for their consent to be followed-up as they come back for their clinical appointment or at home within 1-month of the “exit” interview to participate in a follow-up interview. To facilitate follow-up of cohort participants and individuals who will be selected to participate in qualitative activities, RAs will obtain locator information from consenting individuals, including telephone numbers and home address.

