QIPV 2	In the past 12 months, has your partner		
QIPV 3	Threatened to hurt you, your children or someone close to you?	No; Yes; Don't know	0;1; -1
QIPV 4	Hit, slapped, kicked, pushed, shoved or otherwise physically hurt you?	No; Yes; Don't know	0;1; -1
QIPV 5	If yes, in the past 12 months how many times has this happened to you?	Once; Twice; Three times; Four times; or more times; I don't know	1;2;3;4;5; -1
QIPV 6	In the past 12 months, has you're your partner insulted you or made you feel bad about yourself?	No; Yes; Don't know	0;1; -1
QIPV 6a	If yes, in the past 12 months how many times has this happened to you?	Once; Twice; Three times; Four times; or more times; I don't know	1;2;3;4;5; -1
	If yes to any of the above questions, the lay counsellor should inform the possible social harms that may occur and establish if it is safe to give an individual a test kit their partner.		
Section 6: Questions on gender norms			
QSN 0	Please indicate how strongly you agree or disagree with the following statements.		
QSN 1	"It is normal for a woman to start the discussion with the partner on HIV testing"	Strongly agree; agree; disagree; Strongly disagree	1;2;3;4
QSN 2	It is normal for a woman to ask her male partner to go for HIV testing: agree, disagree	Strongly agree; agree; disagree; Strongly disagree	1;2;3;4
QSN 3	"It is normal for the partner/husband to beat or insult	Strongly agree; agree;	1;2;3;4

	the wife if she has done something wrong. Such as giving him an HIV self-testing kit”	disagree; disagree	Strongly
Section 7: Screening Questions on Alcohol and Drug Use			
Alcohol_0	I will now ask you questions about drinking alcohol and drug use. I know these questions are sensitive and want to remind you that your answers are completely confidential. Do you have any questions before we begin?		
Alcohol_1	How often do you have a drink containing alcohol?	Never; Monthly or less; 2 to 4 times a month; 2 to 3 times a week; 4 or more times a week	1; 2; 3; 4; 5
Alcohol_2	How many drinks containing alcohol do you have on a typical day when you are drinking?	1 or 2; 3 or 4; 5 or 6; 7, 8, or 9; 10 or more	1; 2; 3; 4; 5
Alcohol_3	How often do you have six or more drinks on one occasion?	Never; Less than monthly; Monthly; Weekly; Daily or almost daily	1; 2; 3; 4; 5

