SHS_Fu_2	Has anything good happened to you or in your relationship which you think was a result of you talking about HIV testing or giving the test to your partner	Yes; No; Don't know	
SHS_Fu_2a	If yes; What was good? ( tick all that are relevant)	Discussed HIV; Was able to tell my partner my HIV status; Know my partners HIV status; Felt more comfortable with my partner; Felt more able to discuss issues with my partner; My partner was more loving/caring; Resolved some of our issues in our relationship Other ( free text)	
SHS_Fu_3	From the time your partner received the HIV self-testing kit, Has your partner ever.....		
SHS_Fu_3a	Pushed, grabbed, slapped, choked, hit or kicked you?	Yes; No; Don't know	1; 2; 3
SHS_Fu_3b	Threatened to hurt you, your children or someone close to you?	Yes; No; Don't know	1; 2; 3
SHS_Fu_3c	Insulted you or made you feel bad about yourself?	Yes; No; Don't know	1; 2; 3
SHS_Fu_3d	Taken away money or resources that you/your children need to survive?	Yes; No; Don't know	1; 2; 3
SHS_Fu_3e	Threatened to divorce you?	Yes; No; Don't know	1; 2; 3

SHS_Fu_3f	Sent you back to your family home?	Yes; No; Don't know	1; 2; 3
SHS_Fu_3g	Forced you to have sex when you did not want to?	Yes; No; Don't know	1; 2; 3
SHS_Fu_4a	[If yes to any of the above GBV questions] Did this happen as a result of discussing HIV testing with your partner?	Yes; No; Don't know	1; 2; 3
SHS_Fu_4b	Do you think any of these things were the result of having offered an HIV self-test to your partner?	Yes; No; Don't know	1; 2; 3

**Follow-up questionnaire for secondary distribution cohorts – questionnaire for intended user of secondary distribution HIVST kit**

Section 0: Preparing for the survey			
Variable Name	Question	Option	Option codes
PS 1	What is the date today?	[time stamp]	
PS 1a	CLINIC NAME	[EDC CODE]	
PS 2	Scan participant barcode		
PS 3	Which community are you in?	Community 1	1
		Community 2	2
		Community 3	3
		Community 4	4
		Community 5	5
		Other	Specify
PS 4	What models of HIV self-testing distribution are in this community? [tick all that applies]	VMMC	1
		Community- or facility led	2
		Secondary distribution through ANC	3
		Secondary distribution through ARTHIV testing and treatment services	4
		Workplace	5
		Other (Specify)	6
PS 5	Through which distribution model was the client offered an HIV self-testing kit?	Secondary distribution through ANC	3
		Secondary distribution through ART	4

Section 1: Consenting Process			

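### Four of the seven partner acts asked about at follow-up, including forced sex, have no counterpart in the exit interview, so history of gender-based violence is measured incompletely and those harms have no baseline

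*Protocol*

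**What the plan says.** Section 4.3.2 of the protocol names "history of gender based violence and clinic from which the Index was recruited" among the individual- and couple-level factors for the cohorts. Section 5.2 says that the exit interview will collect "details about their relationship with their partner including questions about gender based violence".

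The tool is in Appendix 3, exit interview, Section 5. QIPV 1 asks about an expected reaction to the clinic visit ("will receive will include HIV testing, would he react angrily or negatively"). The acts are then introduced by "In the past 12 months, has your partner" and cover threats (QIPV 3), physical acts (QIPV 4: "Hit, slapped, kicked, pushed, shoved or otherwise physically hurt you") and insults (QIPV 6). An instruction to the lay counsellor about possible harms and the safety of giving a kit follows, and applies if any of these questions is answered yes.

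The follow-up questionnaire for the secondary distributor asks about seven acts since the partner received the kit (SHS_Fu_3a to 3g). They include "Taken away money or resources that you/your children need to survive" (3d) and "Forced you to have sex when you did not want to" (3g), and the next item refers to the set as GBV questions. The social harms grading table in Appendix 4 puts denied household resources in Grade 1, psychologically coercive sex in Grade 2 and physically coercive sex in Grade 3.

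**The concern.** The protocol's own follow-up form and grading table treat forced sex and withheld resources as violence or harm, but the baseline tool does not ask about either. Three things are affected.

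- **Exposure.** A participant whose only exposure is one of the unasked acts may be placed with those who have no history of violence, which blurs the comparison.
- **Interpretation of harm.** Objectives 4 and 12 concern the frequency of social harms and the factors behind them. For an act that was not asked about at baseline, a report at follow-up cannot be compared with what the relationship was like before the kit.
- **Safety instruction.** It is tied to the Section 5 answers, so the same participant may not meet it.

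An act that was never asked about at exit cannot be recovered in the analysis.

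**Working it through.** The plan states no figure for this point. The check is a comparison of items, followed by an illustration of size.

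**Items side by side**

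| Act | Exit interview | Follow-up |
|---|---|---|
| Physical acts | QIPV 4 | 3a |
| Threats to hurt | QIPV 3 | 3b |
| Insults | QIPV 6 | 3c |
| Taken money or resources | none | 3d |
| Threatened divorce | none | 3e |
| Sent back to family home | none | 3f |
| Forced sex | none | 3g |

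Three of seven acts are matched, so 7 − 3 = 4 are not. The absence applies to every participant.

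The exit items nearest in content lie elsewhere: control of money (DM_3, DM_4), regard for sexual wishes and say over sex (CCS_3, CCS_5), expected violence over condom use (SRP_2). They measure decision power or hypothetical reactions rather than acts, and they come after the safety instruction.

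**Is the gap only provisional?** The note at the head of Appendix 3 says that response options, order and skip patterns may change, and that the forms are printed to show the wording of the questions. A missing question is not covered by that note.

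**Illustrative size in the factor analysis**

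Inputs:
- n = 300 followed index patients per cohort (Section 5.4).
- P = 25% true past-year violence: assumed.
- x = share of the exposed with unasked acts only: assumed 10%, 20% or 40%.
- Partner use of 60% in the unexposed and 40% in the exposed. Section 5.4 gives these values for knowledge of partner status and for disclosure, not for violence; they are borrowed here for scale.
- Missed participants are assumed to have the same partner use as other exposed participants, and nobody unexposed is assumed to be classed as exposed.

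Misclassified = n × P × x:
- x = 10%: 300 × 0.25 × 0.10 = 7.5
- x = 20%: 300 × 0.25 × 0.20 = 15
- x = 40%: 300 × 0.25 × 0.40 = 30

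Observed use in the apparent unexposed group = (0.75 × 0.60 + 0.25x × 0.40) / (0.75 + 0.25x). Subtracting 0.40 gives the observed contrast:
- x = 10%: 0.460/0.775 = 0.594, contrast 19.4 points
- x = 20%: 0.470/0.800 = 0.5875, contrast 18.8 points
- x = 40%: 0.490/0.850 = 0.576, contrast 17.6 points

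The loss is 0.6 to 2.4 points out of 20. A second grid, with P from 20% to 40%, and 5% to 20% of the exposed missed through forced sex alone, gives contrasts of 17.7 to 19.8 points.

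**The case against.** The strongest reply is that the gap has limited consequences, and much of it stands.

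- **Attribution has other supports.** The follow-up acts are anchored to the time since the partner received the kit. SHS_Fu_4a and 4b ask whether the acts resulted from discussing testing or from offering the self-test, and Section 8.4 has the study PI judge relatedness. A reader might infer that harms tied to HIVST will be overstated, or cannot be attributed at all. The documents do not support that. The narrower point remains: 4a and 4b record the participant's opinion, asked once for the whole set of acts, and neither they nor the PI can draw on a baseline for these four.
- **No coding rule is given.** A reader might infer that forced sex is coded as no violence at baseline. It is simply not asked, no composite is defined, and the derivation may properly sit in an analysis plan. Any composite must, however, be built from the items that were asked.
- **Section 5 catches some of these participants.** QIPV 1 counts towards the instruction, the catch-all ending of QIPV 4 may capture some physically forced sex, and QIPV 6 is broad. The documents give no size for the remainder.
- **The instruction is not the only safeguard.** Sections 8.4 and 10.2 describe mitigation at distribution, support information, referral and community reporting. A reader might infer that these participants go unprotected; the text does not show that.
- **The factor is one of many.** Section 7.3 explores several factors, and the sample size does not rest on this one.

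None of this supplies the missing items. The argument that the questions are too sensitive is weak, because the same participants are asked them about a month later by trained staff, with a right to decline.

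**Conclusion.** The point holds as a mismatch between two of the protocol's own questionnaires. The exit interview covers three of the seven acts that the follow-up form groups as gender-based violence. Forced sex and taken resources, which correspond to harms in the grading table, are among the four left out. Some participants exposed only to the omitted acts may therefore be classed as unexposed and may not meet the Section 5 instruction, and follow-up reports of these acts have no baseline.

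The expected bias in the factor analysis is small: 0.6 to 2.4 points on an assumed 20-point contrast. That size rests on assumed prevalences, an assumed share missed and a contrast borrowed from other factors, so it shows scale only. The better reasons to act are the interpretation of follow-up harm and agreement between the tools. This is a cheap improvement that must be made before the exit interviews; it does not threaten the primary outcome or the sample size.

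**What to change.** 1. Add the wording of SHS_Fu_3d to 3g to Section 5 of the exit interview, with the 12-month recall already used there. At a minimum, add 3g (forced sex) and 3d (taken resources). If 3e and 3f are left out, say that they have no baseline.
2. Include forced sex and taken resources when deriving history of gender-based violence.
3. Report each follow-up act split by whether the same act was reported at baseline, alongside the answers to SHS_Fu_4a and 4b.
4. The sponsor should reconcile the Section 5 safety instruction with the acts that the grading table counts as harms. Which answers should lead to that instruction is the sponsor's decision and is not proposed here.

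The cost is two to four more sensitive questions, a slightly longer interview and some refusals. Staff training on such questions and the option to decline are already provided for in Section 8.4.
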